## 8. PROCEDURES FOR RESEARCH STUDY

Table 1: Study Schedule of Events for Study Subjects

Variables	Pre – Study Imaging	Study Imaging	Post- Study imaging
Informed Consent	X		
Entry Criteria	X		
Demographic Information a	X		
Review relevant Medical/Surgical History	X		
DBT Imaging	X		
Collection of two-view FFDM Imaging b	X	X	
Repeat of DBT or FFDM Imaging c		X	
Safety Assessments (AE, SAE, device malfunctions) d		X	
Image assessment by site radiologist			X
Histopathology			X

DBT = Digital Breast Tomosynthesis; FFDM = Full field digital mammography; AE = adverse event; SAE = serious adverse event;

a: Including age, menopausal status. b: FFDM imaging may be acquired at either time point.

c: Only if prior two-view screening and/or diagnostic images are not available or were not obtained on a GE system. d: Device-related AEs and SAEs reported.

### 8.1. Pre-Study Imaging Procedures

All enrolled subjects will undergo the following procedures prior to receiving their additional study-specific DBT and/or FFDM imaging, as necessary:

- A notation will be made in the subject's medical chart that the subject is participating in the clinical trial. Additionally, the notation should indicate the subject had her questions answered, and that she has read, signed, dated and received a copy of the Informed Consent Form (ICF);
- Study entry criteria, demographic information (including age), relevant reproductive medical/surgical history such as oophorectomy, hysterectomy, or other reproductive surgeries and pregnancy/menopausal status will be reviewed;
- A subject number will be assigned.

There is no special subject preparation required to perform DBT or FFDM mammography.

### 8.2. Digital Breast Tomosynthesis (DBT) and Full Field Digital Mammography (FFDM) Examinations

Prior screening DBT and screening/diagnostic FFDM images will be collected from each subject's medical record. If prior screening and/or diagnostic images/views are not available or were not collected with GE equipment, a subject will undergo study-specific DBT and/or FFDM imaging, as needed. Study-specific imaging may include bilateral 2-view (CC/MLO) FFDM and/or DBT (as needed) performed using GE systems available at the site and according to the site's standard procedures.

Two-view DBT and two-view FFDM image acquisition (both CC and MLO views) on GE equipment shall be performed within 30 days of each other, regardless if FFDM or DBT was performed before or after the patient agreed to participate in the study. Subjects requiring study-specific imaging will undergo the following procedures:

- Enter a changing room to prepare for their mammogram;
- Each subject of child-bearing potential shall wear a lead apron or have equivalent shielding during the DBT and/or FFDM procedures;
- Undergo DBT and/or FFDM procedure(s);
- Will be monitored for AEs and SAEs from study-specific DBT and FFDM and will be recorded in the source document and CRF. Device malfunctions shall be sent to the Sponsor as per Section 12.5 Management of Device Complaints.

All scanning should be performed within the standard range of scan parameters, as per the manufacturer-provided operator's manual(s) for GE FFDM and DBT devices. The scan operator should conduct DBT and FFDM exams according to the standard clinical practice at the site with consideration for:

- Subjects with large breasts, because perspiration under the breast can cause the skin to soften, and become paper-thin;
- Any existing condition that may cause unusual discomfort or tearing of the skin, which could include telling the subject the importance of correct positioning. The subject should be positioned carefully to avoid any discomfort to abnormalities such as warts, scarring, or skin which is not intact;
- Warmth of the breast support surface, which can be warm to the touch, as it contains electronic components that generate heat;
- Positioning the breast properly in FFDM and DBT in the CC position, where it is essential that the breast is lifted away from the chest wall and gently pulled forward, in order to visualize the maximum amount of breast tissue.

### 8.3. Post-Study Imaging Procedures

The following assessments will be performed:

- DBT and FFDM images will be assessed at the study site by one or more MQSA-qualified radiologists, as per institutional standard practice;
- If clinically indicated based on imaging results, subjects will undergo biopsy or surgical intervention with breast tissue histopathological analysis, as per institutional standard practice;

The IDI MammoWorkstation permits 3-D-reconstruction and 2-D-reconstruction (V-Preview). The evaluating radiologist should use the image reconstruction views appropriate for diagnostic evaluation, per his or her medical judgment, and handle diagnostic evaluations in accordance with the standard of care at the investigational site.

### **8.3.1. On-Site Image Interpretation**

DBT and FFDM images of all included subjects will be assessed at the study site by one or more MQSA-qualified radiologists on an IDI MammoWorkstation. The FFDM and/or DBT results may result in a recommendation that additional breast lesions be biopsied (in addition to that/those already planned when the patient entered the study). If so, biopsy plans may be changed accordingly.

The evaluating radiologist(s) at the site will record for each subject, the following parameters:

- Breast density (as defined by BI-RADS® density categories);
- Finding characteristics, to include breast laterality, lesion type, depth, quadrant and size. In the case of multiple findings, a maximum of three (3) most suspicious findings will be scored and localized;

### **8.3.2. Additional Diagnostic Imaging**

If a subject is called back for further diagnostic assessment, the additional breast imaging that the subject undergoes will be recorded on the CRF.

## **8.4. Biopsy Procedures**

Percutaneous and open surgical breast interventions will proceed as per standard of care at the recruiting site. The interpretation of the local pathologist will be recorded on the CRF.

If the subject does not complete the biopsy procedure as scheduled or if the biopsy procedure is not successful or produces indeterminate results that are not able to be resolved by clinically indicated procedures, such as repeat biopsy(ies), the subject will be withdrawn.

For benign/negative histopathology results, the site radiologist will review the subject's imaging and histopathology findings for concordance, per the site's standard of care, and results will be captured on a CRF. Histologic concordance with imaging for negative or benign lesions will be considered truth for non-cancer status. If surgical excision is recommended even after concordance between imaging and histopathology, the resulting histopathology from surgical excision may be collected as part of the study.

Subjects who have negative or benign histology findings that are discordant with imaging shall be followed-up per the site's standard of care. If rebiopsy is recommended, the histology findings and concordance assessment of the rebiopsy will be used to determine the subject's cancer status. If rebiopsy is not recommended or if histopathology remains discordant with imaging findings after rebiopsy, the subject will be withdrawn from the study.

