## 5. OBJECTIVES OF RESEARCH STUDY

### 5.1. Hypothesis

No statistical hypothesis is tested in this data collection study. The sample size for DBT-screened women who are ultimately referred for breast biopsy in this study is determined to provide sufficient accrual of cancer cases for a subsequent statistically powered analysis as part of a separate protocol (ADAPT-BIE).

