## **8.5. Follow-up Procedures**

Results from surgical intervention and/or any additional follow-up resulting from biopsy(ies) (e.g., breast ultrasound or breast MRI) will be considered in determining truth of cancer status. No additional follow-up appointments will be required for subjects that have completed biopsy/surgical intervention with positive findings or documented histologic concordance with imaging.

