## **8.7. Withdrawal and Discontinuation Criteria**

### **8.7.1. Subject Withdrawal Rules**

The subject's medical care shall take precedence over any research imaging or other procedures associated with the study. If it is discovered during the study (any time after consent has been signed or study procedures have begun) that any study procedure will negatively impact required clinical care, the subject shall be withdrawn from the study.

Each subject is free to withdraw from the study at any time. Investigator(s) also have the right to withdraw subjects from the study in the event of illness, AEs, SAEs, or other reasons concerning the health or well-being of the subject, or in the case of lack of cooperation.

If a subject withdraws (or is withdrawn), all efforts will be made to complete and report the observations up to the time of withdrawal. A complete final evaluation at the time of the subject's withdrawal should be made and an explanation given on the CRF given as to why the subject is withdrawing or being withdrawn from the study. If the reason for withdrawal is a clinical AE or SAE, monitoring will continue until the outcome is evident. The specific event or test result(s) must be recorded on the CRF.

In the event the subject experiences pain, undue discomfort, or destabilizing vital signs that is observed by visual inspection or via monitoring equipment, or requests to discontinue study procedures, the study procedures will be stopped immediately, and the appropriate response will be taken according to the standard of care at the investigational site.

A subject may withdraw from study participation at any time, for any reason without consequence. The study staff may withdraw a subject at any time for any reason. There shall be no negative repercussions to the subject. The reasons for withdrawal and discontinuation for any subject shall be recorded. These will be reported to the Sponsor. The EC/IRB should be notified per their notification of subject withdrawal policy.

As described in Section 8.4 Biopsy Procedures, subjects with initial benign/negative histopathology results that are discordant with imaging findings will be withdrawn from this study if rebiopsy is not recommended, or if histopathology remains discordant with imaging findings following rebiopsy.

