## 10. DATA ANALYSIS AND STATISTICS

### 10.1. Statistical Analysis Methods

#### 10.1.1. Sample Size Justification

The projected sample size is determined by the need to accrue at least 120 cancer cases and 250 non-cancer cases for the overall GE Healthcare SenoClaire® - GE Breast Tomosynthesis (DBT) development program. To achieve these overall accrual targets, the data from this study will be pooled with data from other studies (e.g. ADAPT-SCR and ADAPT-BX).

In this study, for an enrollment of 200 subjects recommended for breast biopsy, it is assumed, based on the GE-190-003 experience, approximately 33% are expected to have a proven cancer

and approximately 33% will have a benign lesion. So, at least 66 cancer cases and 66 non-cancer cases are expected to be accrued in this study. Up to 200 subjects referred for breast biopsy (enrollment ceiling per site will be 120 subjects) will be enrolled from up to two (2) centers located in the US until approximately 70 histopathology-confirmed cancers have been accrued. Enrollment will be managed to ensure equitable accrual of subjects across sites, if applicable.

Based on the GE-190-001 experience, for an enrollment of 250 subjects having screening mammography, about 185 (75%) will complete the study with a normal 1-year follow-up. Approximately 2% are expected to have a proven cancer either at screening or during follow-up, which will provide an estimated 6 cancer cases; expected to be accrued in the ADAPT-SCR protocol.

In the ADAPT-BX study, for a target enrollment of 275 subjects recommended for breast biopsy, it is assumed that, based on the GE-190-003 experience, approximately 33% are expected to have a proven cancer and approximately 33% will have a benign lesion. So, at least 90 cancer cases and 90 non-cancer cases are expected from the ADAPT-BX accrual.

Thus, in the combined ADAPT-SCR and ADAPT-BX protocols, it is expected that about 90 cancer cases and 250 non-cancer cases will be accrued, in which cancer cases were predominantly flagged using FFDM. To reduce the bias from the FFDM screening exam, cancer cases initially flagged using DBT will be accrued from this protocol, until at least 120 eligible cancer cases are accrued between the three protocols.

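### Sections 8.4 and 8.7.1 withdraw women whose benign-discordant result is not resolved by rebiopsy, although 8.5 counts later surgery and follow-up toward truth, so cases are lost according to how the images looked

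*Combined protocol and SAP*

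**What the plan says.** Section 8.4 sets the truth rule after biopsy. Benign or negative histology that agrees with the imaging is truth for non-cancer. Where it does not agree, the findings "that are discordant with imaging shall be followed-up per the site" (the sentence goes on to that site's usual care). If rebiopsy is recommended, its histology and concordance settle the woman's status and she stays in. Otherwise: "If rebiopsy is not recommended or if histopathology remains discordant with imaging findings after rebiopsy, the subject will be withdrawn from the study".

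Section 8.7.1 restates this: such subjects "will be withdrawn from this study if rebiopsy is not recommended, or if histopathology remains discordant with imaging findings following rebiopsy". For withdrawn subjects it asks for observations up to the point of withdrawal. Monitoring continues beyond that only when an adverse event was the reason.

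Section 8.5 says that surgical results and "any additional follow-up resulting from biopsy(ies) (e.g., breast ultrasound or breast MRI) will be considered in determining truth of cancer status". It makes no exception for discordant cases. Section 6.2 runs each subject's participation from enrollment until her cancer status is determined.

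The Efficacy Population in 10.1.2 is defined by eligibility, protocol violations and image availability. It mentions neither truth status nor withdrawal. Section 10.1.3 summarizes withdrawals overall, by site and by modality, but not by reason. Section 10.3 rules out imputation.

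**The concern.** When histology is benign, discordance ordinarily means that the imaging looked more suspicious than the tissue result. Concordance is judged against the same DBT and FFDM images that ADAPT-BIE will compare. Benign cases whose images fit the histology stay, and those whose images did not fit, and were not settled by rebiopsy, leave. Selection into the case set then depends on image appearance, which is what the reader study measures. Section 6.3 names selection bias as something this protocol is meant to reduce, but does not mention this route.

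Two kinds of case are exposed: non-cancers that looked suspicious, and cancers that the biopsy missed and that surface only at surgery or later work-up. The second kind matters in a protocol whose purpose is to accrue cancers. Section 8.5 would accept the evidence in both, but 8.4 and 8.7.1 as written can end participation before it is used.

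**Working it through.** **1. The passages side by side**

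| Situation after benign or negative biopsy | 8.4 and 8.7.1 | 8.5 and 6.2 |
|---|---|---|
| Concordant | Kept as non-cancer | Consistent |
| Discordant, rebiopsy positive, or benign and concordant | Kept, status from rebiopsy | Consistent |
| Discordant, still discordant after rebiopsy | Withdrawn | Later surgery or imaging counts toward truth |
| Discordant, rebiopsy not recommended | Withdrawn | Surgery or follow-up imaging counts toward truth |

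The conflict is confined to the last two rows. Section 8.4 does not say when withdrawal takes effect relative to the usual-care follow-up it describes just before. It provides for collecting surgical histology only after a concordant result, and does not say whether excision after a discordant result counts as rebiopsy. A woman who goes to surgery instead of rebiopsy is therefore withdrawn on a literal reading, even if surgery finds cancer.

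**2. The plan's own figures (section 10.1.1)**

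The plan takes the case "for an enrollment of 200 subjects recommended for breast biopsy", of whom "approximately 33% are expected to have a proven cancer" and "approximately 33% will have a benign lesion".

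- Cancers: 200 × 0.33 = 66. Non-cancers: 200 × 0.33 = 66. Both stated figures reproduce.
- In neither class: 200 − 66 − 66 = 68, or 68/200 = 34%.

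The plan does not break the 68 down by reason. They would include uncompleted, failed or indeterminate biopsies as well as unresolved discordance. The number is at most a ceiling on the discordance losses that the plan's assumptions allow, and not an estimate of them.

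**3. Illustration of size (every rate here is an assumption)**

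Let W be the number of withdrawn non-cancers, N the non-cancers kept, and d the amount by which specificity is lower in the withdrawn. The share withdrawn is w = W/(N + W), and the overstatement of specificity is w × d.

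- Women without proven cancer: 200 − 66 = 134.
- If 5% to 10% end unresolved: 134 × 0.05 = 6.7 and 134 × 0.10 = 13.4, about 7 to 13 women.
- With d = 30 points and N = 250, the program target: 7/257 = 2.7%, × 30 = 0.8 points; 13/263 = 4.9%, × 30 = 1.5 points.
- If only 1% end unresolved: 134 × 0.01 = 1.3, about one woman; 1/251 = 0.4%, × 30 = 0.1 points.

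These figures treat every withdrawn woman as a non-cancer. Any who have cancer belong in a separate count, so a lost-cancer figure cannot be added on top.

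**4. Direction**

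Dropping non-cancers that looked suspicious on a modality raises its apparent specificity and AUC. Dropping true cancers that looked suspicious on it lowers its apparent sensitivity and AUC. The documents give neither the mix of the two nor the modality that drove the discordance.

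**The case against.** The strongest reply is that leaving out cases without established truth is a defensible design choice, that the group is small, and that the protocol already handles part of it. Rebiopsy-resolved women are kept, including cancers found at rebiopsy. Concordance results and withdrawal reasons go on the CRF, and withdrawn women still count as enrolled. Section 8.4 mentions usual-care follow-up before withdrawal, so a site could apply 8.5 first. Section 5.1 says "No statistical hypothesis is tested in this data collection study", and 10.1.1 expects ADAPT-SCR and ADAPT-BX alone to supply about 250 non-cancers. How this protocol's non-cancers are used is set in ADAPT-BIE, which is not available here and may already contain a sensitivity analysis.

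Much of this stands. It limits the point to an unresolved subset and rules out a confident statement of size. It does not remove the conflict: a site cannot tell from the text whether to withdraw or to wait for a result that 8.5 accepts, and 10.1.2 does not say what happens to the images.

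Four stronger readings might be inferred, and the documents do not support them:

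- That all benign-discordant cases are withdrawn. Only those not settled by rebiopsy are.
- That all missed cancers are lost. Those found at rebiopsy are kept. Those missed by a biopsy judged concordant also stay, but labelled non-cancer, which is misclassification and not removal.
- That the rule favors DBT because women enter through suspicious DBT screening. Concordance is judged against the subject's imaging as a whole, and the two effects in step 4 pull in opposite directions.
- That a proven cancer could be withdrawn because of a second, discordant lesion. The synopsis makes positive histology truth of cancer. Section 8.3.1 scores up to three findings and 8.4 acts on the subject, so the gap is one of wording only.

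**Conclusion.** The point holds in a limited form and should be fixed. Sections 8.4 and 8.7.1 conflict with 8.5 and 6.2 for women whose benign-discordant result is not resolved by rebiopsy. Followed literally, the rule removes them according to how the images under comparison looked, together with any cancer among them found by surgery or later work-up.

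The documents do not yield the number affected, the size of the bias or its direction for DBT against FFDM. The 0.8 to 1.5 specificity points are purely illustrative. They rest on an assumed 5% to 10% unresolved rate, an assumed 30-point deficit, and all withdrawn women being non-cancers, set against 250 pooled non-cancers. A larger shift in the pool would need the same rule and rate in the other ADAPT protocols, which cannot be seen. At a 1% rate the effect is close to nil.

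**What to change.** 1. In 8.4 and 8.7.1, set a discordant subject's truth status under 8.5 from any surgical or follow-up result already obtained under the site's usual care and available by a stated data cut-off. Apply this alike to malignant and benign outcomes.
2. Class subjects still unresolved at the cut-off as 'truth status indeterminate' in place of withdrawing them. Retain their images and data, and leave them out of the cancer and non-cancer counts.
3. In 10.1.2, state the status of these subjects. In 10.1.3, tabulate them by reason, lesion type and breast density.
4. Flag them to ADAPT-BIE for a sensitivity analysis that classes them first as non-cancer and then as cancer. That analysis belongs there, since this protocol is descriptive only.
5. State in one sentence that positive histology for any lesion makes the subject a cancer case.

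The cost is protocol wording, a chart look-up and image handling for a few women, and one table. Section 15.3 already lets the sponsor request clinical imaging and biopsy results from the study period. Clinical follow-up does not change. One limitation remains: outcomes known by the cut-off may themselves be selective, because malignancy can be proven sooner than benignity without rebiopsy. The unresolved remainder must therefore be reported beside the resolved cases.

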## **8.5. Follow-up Procedures**

Results from surgical intervention and/or any additional follow-up resulting from biopsy(ies) (e.g., breast ultrasound or breast MRI) will be considered in determining truth of cancer status. No additional follow-up appointments will be required for subjects that have completed biopsy/surgical intervention with positive findings or documented histologic concordance with imaging.

## **8.6. Incidental Findings**

If any unexpected atypical or abnormal findings unrelated to the study aims (breast cancer identification) are identified during this study that may incidentally indicate other diseases or other unknown conditions, these cases will be reported to the Site Principal Investigator. If the Site Principal Investigator determines that these findings are medically significant in his or her medical judgment, he or she will notify the subject and refer her for further follow-up outside of this study according to the standard of care at the investigational site. Follow-up for incidental findings is not required by this study, but relevant images and data resulting from examinations related to incidental findings may be provided to the Sponsor, at the discretion of the Principal Investigator, if determined to be relevant to study conduct or integrity of study results.

## **8.7. Withdrawal and Discontinuation Criteria**

### **8.7.1. Subject Withdrawal Rules**

The subject's medical care shall take precedence over any research imaging or other procedures associated with the study. If it is discovered during the study (any time after consent has been signed or study procedures have begun) that any study procedure will negatively impact required clinical care, the subject shall be withdrawn from the study.

Each subject is free to withdraw from the study at any time. Investigator(s) also have the right to withdraw subjects from the study in the event of illness, AEs, SAEs, or other reasons concerning the health or well-being of the subject, or in the case of lack of cooperation.

If a subject withdraws (or is withdrawn), all efforts will be made to complete and report the observations up to the time of withdrawal. A complete final evaluation at the time of the subject's withdrawal should be made and an explanation given on the CRF given as to why the subject is withdrawing or being withdrawn from the study. If the reason for withdrawal is a clinical AE or SAE, monitoring will continue until the outcome is evident. The specific event or test result(s) must be recorded on the CRF.

In the event the subject experiences pain, undue discomfort, or destabilizing vital signs that is observed by visual inspection or via monitoring equipment, or requests to discontinue study procedures, the study procedures will be stopped immediately, and the appropriate response will be taken according to the standard of care at the investigational site.

A subject may withdraw from study participation at any time, for any reason without consequence. The study staff may withdraw a subject at any time for any reason. There shall be no negative repercussions to the subject. The reasons for withdrawal and discontinuation for any subject shall be recorded. These will be reported to the Sponsor. The EC/IRB should be notified per their notification of subject withdrawal policy.

As described in Section 8.4 Biopsy Procedures, subjects with initial benign/negative histopathology results that are discordant with imaging findings will be withdrawn from this study if rebiopsy is not recommended, or if histopathology remains discordant with imaging findings following rebiopsy.

Subjects withdrawn after consent is signed will be counted as enrolled subjects up until the time of withdrawal, and will be considered in reporting total enrolled subjects in this study per the populations defined in Section 10.1.2. - Study Populations.

